### Information to be Collected on Screening Failures

The informed consent date, demographics, and reason the subject did not qualify for the study will be collected for all subjects determined to be screen failures. Adverse events experienced by screen failure subjects will be collected from the date of signing consent to the day the subject is confirmed to be a screen failure. This information will be captured in the subject's source documents and appropriate eCRF(s).

## 6.2. Treatment Period

The subject will begin treatment upon confirmation of eligibility. Phase 1b subjects will be enrolled into the appropriate cohort and for Phase 2 IDH2 subjects will be randomized in a 2:1 fashion to receive either oral AG-221 + SC azacitidine or SC azacitidine alone.

[figure not shown]
Subjects should continue to be eligible for study entry prior to the start of study treatment on Day 1 of Cycle 1. Study Treatment is to be initiated on Day 1 of each treatment cycle. Unless noted otherwise, an administrative window of  $\pm 3$  days is permitted for all subsequent visits after the start of study treatment in each treatment cycle in the Treatment Phase. Day 1 of Cycles 2 and

beyond may be delayed from Day 28 of the prior cycle in order for subjects to recover from toxicity and meet criteria for initiating each treatment cycle. Treatment cycles are 28 days in duration, and will occur as described in Section 7.2.

The following evaluations will be performed at the frequency specified in the Table of Events (Table 4) or more frequently if clinically indicated. The evaluations should be performed prior to dosing on scheduled clinical visit day, unless otherwise specified. For each evaluation, the same parameters as required at screening or on Day 1 of Cycle 1 should be evaluated.

- Registration of the start of each treatment cycle in IWRS
- HRQoL outcomes (EORTC QLQ-C30 and EQ-ED-5L questionnaires; see Section 6.8)
- Study drug accountability (where applicable; also refer to Section 7.5)
- Study drug dispensing and administration (where applicable; refer to Section 7)
- ECOG performance status
- Physical examination, vital signs and body weight. Significant findings are to be reported on the appropriate eCRF page.
- Body surface area calculation per the Dubois & Dubois formula:  $BSA (m^2) = \text{weight (kg)}^{0.425} \times \text{height (cm)}^{0.725} / 139.2$
- The following laboratory assessments will be done locally:
  - ECHO or MUGA scan if clinically indicated
  - 12-lead ECG. Abnormal finding(s) will be reported on the appropriate eCRF page.
  - For FCBP only, a serum  $\beta$ -hCG pregnancy test (sensitivity of at least 25 mIU/mL) is to be done within 72 hours prior to study treatment administration on Day 1 of each treatment cycle (note that the central serum pregnancy test at screening can be used as the test prior to the start of study treatment in the Treatment Phase if it is performed within the 72-hour timeframe). The subject may not receive study treatment until the investigator has verified that the test result is negative.
- The following laboratory assessments will be done centrally:
  - Urinalysis and/or coagulation test if clinically indicated
  - Hematology panel
  - Chemistry panel
  - Cardiac marker troponin T
  - Fasting lipid panel including total cholesterol, low-density lipoprotein cholesterol (LDL-C), high-density lipoprotein cholesterol (HDL-C), triglycerides
- Continuous evaluations of AEs, [REDACTED] concomitant medications and procedures, and transfusions

- Clinical site staff should confirm if any transfusions were received by the subject (including any at outside local institutions in between study visits) prior to each IP administration via use of patient diary or other local procedure in place at the investigational site.
- Bone marrow aspirate (or biopsy if adequate aspirate is not attainable) samples will be collected for assessing response. The site needs to ensure peripheral blood for central hematology is collected and sent at the time of every bone marrow collection. As specified in the Table of Events ([Table 4](#)), the frequency is within 7 days prior to study treatment administration on Cycles 2, 3, and every 2nd cycle thereafter (eg, Cycles 5, 7, 9, etc), and if clinically indicated (eg, confirmation of CR/CRi/CRp morphologic relapse after CR/CRi/CRp, or progression by a repeated bone marrow assessment at least 1 month later) or required for toxicity assessment. A bone marrow biopsy can be collected in conjunction with an aspirate if it is standard institutional practice or if clinical indicated (eg, evaluation of bone marrow cellularity). Whenever a bone marrow sample is collected, a peripheral blood smear is to be prepared. In addition, whenever a bone marrow aspirate is obtained for confirming CR/CRi/CRp, morphologic relapse after CR/CRi/CRp, or progression, a standard cytogenetic metaPhase preparation will be prepared and sent to the local laboratory for cytogenetic analysis. A bone marrow biopsy can be used for cytogenetics testing if adequate aspirate is not attainable (note that specific handling of the biopsy is required for cytogenetics testing). Bone marrow aspirate and/or biopsy, and peripheral blood smear collected after the start of study treatment for response assessment must be available for both local and central pathology review. Instructions for submission slides of bone marrow aspirate (and/or biopsy) and peripheral blood smear for central pathology review are provided in the Study Reference and Study Central Laboratory Manuals for sample collection, processing, storage, and shipment procedures.
- Response to treatment, per modified IWG AML response criteria, and HI will be assessed whenever bone marrow samples are collected for response assessment (see immediately above).
- In the Treatment Phase, bone marrow aspirate sampling for pharmacodynamic assessments will be performed only in subjects of the AG-120 (Phase 1b expansion stage only) / AG-221 (Phase 1b dose-finding and 2 randomized stage) treatment arms whenever bone marrow samples are collected for response assessment (see above) and if sufficient bone marrow material remains

- Peripheral blood sampling for PK assessments will be performed for AG-120 during Phase 1b and AG-221 during Phase 2 as detailed in [Table 6](#), [Table 7](#), and [Table 8](#).

- Peripheral blood sampling for pharmacodynamic assessments will be performed in all subjects.

### 6.2.1. Baseline

Unless noted otherwise for a particular assessment, results obtained just prior to the start of study treatment on Day 1 of Cycle 1 will serve as the baseline values. If not available, the most recent screening results prior to the start of study treatment on Day 1 of Cycle 1 will be considered the baseline values.

Transfusions history includes the type, number of units, reason, and date of transfusions for the 8 weeks prior to the start of study treatment on Day 1 of Cycle 1.

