### **Phase 2 AG-221 Randomized Stage**

The Phase 2 stage is an open-label randomized study to evaluate the efficacy of oral AG-221 with SC azacitidine versus SC azacitidine alone in order to assess the overall response rate (ORR) and event-free survival (EFS).

The Phase 2 stage will also consist of 3 periods: 1) screening; 2) treatment; and 3) follow-up.

As with Phase 1b, subject screening procedures will occur during the screening period within 28 days prior to the start of study treatment, but the diagnosis of AML will be performed locally for enrollment and retrospectively confirmed based on a subsequent central pathology review. IDH mutational status will be assessed locally, and for sites without local testing capabilities a referral lab will be identified. A bone marrow aspirate and peripheral blood sample must be sent [REDACTED] to the central lab for potential retrospective confirmation of mutational status. Inclusion in the trial can be based on local IDH testing. Subjects eligible for enrollment are those who are not candidates to receive intensive IC, based on the investigator's judgment, due to the presence of co-morbidities, declining performance status, or other factors.

Following review of eligibility, subjects with newly diagnosed AML with an IDH2 mutation will be randomized to receive oral AG-221 + SC azacitidine (Arm 1) versus SC azacitidine alone (Arm 2) in a 2:1 ratio. Arm 1 will include a minimum of 66 subjects and Arm 2 will include a minimum of 33 subjects, (99 subjects total in both arms).

Subjects will be stratified by primary (ie, de novo) or secondary (progression of myelodysplastic syndrome (MDS) or myeloproliferative neoplasms [MPN], or therapy-related) AML according to the WHO classification ([Appendix B](#)).

Study treatment will start within 3 days of randomization. Assessments during study treatment include efficacy, safety, HRQoL, [REDACTED] pharmacokinetics, pharmacodynamics, [REDACTED].

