### 5. TABLE OF EVENTS

**Table 4: Table of Events**

Events Table covers both Phase 1b & 2 (unless otherwise noted)	Screening Period	Treatment Period a							Follow-up Period a	
	Screening  Days -28 to -1	28-day cycles							EOT b	Follow-up
		Cycles 1 to 2				Cycles 3 to 4		Cycle 5 and beyond		
		Day 1	Day 8	Day 15	Day 22	Day 1	Day 15	Day 1		
Informed Consent	× c	-	-	-	-	-	-	-	-	-
IWRS Subject Status Registration (Phase 1b/2)	×	× d	-	-	-	×	-	×	×	-
Inclusion & Exclusion Criteria	×	× e,f	-	-	-	-	-	-	-	-
Demographics	×	-	-	-	-	-	-	-	-	-
AML Diagnosis	× g	-	-	-	-	-	-	-	-	-
Local Testing of IDH1/ IDH2 Gene Mutations on BMA and PB (In addition, BMA and PB samples to be sent to central lab)	× g	-	-	-	-	-	-	-	-	-
Medical History	×	-	-	-	-	-	-	-	-	-
Prior Medications and Procedures	× h	-	-	-	-	-	-	-	-	-
EORTC QLQ-C30 and EQ-ED-5L	-	×	-	-	-	×	-	×	×	-
ECOG Performance Status	×	×	-	-	-	×	-	×	×	-
Physical Examination i	×	×	-	-	-	×	-	×	×	-
Vital Signs	×	×	×	×	×	×	×	×	×	-

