d The subject should start study treatment (ie, Day 1 of Cycle 1) within 3 days after enrollment or randomization.

e Subject should continue to be eligible for study entry prior to the start of study treatment on Day 1 of Cycle 1.

f Cycle 1 only.

g See Section 6.1 for details regarding collecting BMA, BMB, PBS, and cytogenetics at screening for assessing AML diagnosis, collecting BMA and PB at screening for potential retrospective confirmation of mutational status, and collecting BMA and PB at screening for pharmacodynamics ██████████.

[figure not shown]

[figure not shown]
- h All prior medications (prescription and non-prescription) taken and treatment procedures received from the 4-week period (ie, 28 days) prior to starting study treatment (including those prior to the start of study treatment on Day 1 of Cycle 1) and all prior anticancer therapies, regardless of discontinuation date of treatment.
- i Source documented only.
- j The BSA calculation is per the Dubois & Dubois formula:  $BSA (m^2) = \text{weight (kg)}^{0.425} \times \text{height (cm)}^{0.725} / 139.2$ . The dose should be calculated on Day 1 of each treatment cycle. The dose during a treatment cycle should not be amended.
- k These assessments will be done locally. See Section 6.2 for details.
- l If an assessment has been performed within 28 days prior to the start of study treatment, it does not need to be repeated.
- m Pregnancy test is required for all FCBPs (see Section 4.2 for the definition). Serum  $\beta$ -hCG pregnancy test (sensitivity of at least 25 mIU/mL) will be performed centrally at screening. For FCBP subjects, a local serum  $\beta$ -hCG pregnancy test (sensitivity of at least 25 mIU/mL) is to be done within 72 hours prior to study treatment administration on Day 1 of every treatment cycle in the Treatment Phase and at the EOT Visit. Negative results are required for study treatment administration.
- n These assessments will be done centrally. See Section 6.2 for details.
- o A local serum pregnancy test (sensitivity of at least 25 mIU/mL) is to be done within 72 hours prior to the start of study treatment in the Treatment Phase for FCBP only (note that the screening central serum pregnancy test can be used as the test prior to the start of study treatment in the Treatment Phase if it is performed within the 72-hour timeframe).

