## 6.8. Quality-of-Life

Two instruments, the European Organization for Research and Treatment of Cancer Quality-of-Life questionnaire (EORTC QLQ-C30) and EuroQoL Group EQ-5D-5L, will be used for evaluating HRQoL outcomes.

The EORTC QLQ-C30 ([Aronson, 1993](#)) is a validated quality-of-life measure applicable to subjects with any cancer diagnosis. It is composed of 30 items that address general physical symptoms, physical functioning, fatigue and malaise, and social and emotional functioning. Subscale scores are transformed to a 0 to 100 scale, with higher scores on functional scales indicating better function and higher scores on symptom scales indicating worse symptoms. The EORTC QLQ-C30 is available in many languages. This instrument takes 10 to 15 minutes to administer. The EORTC QLQ-C30 data will be captured using a portable electronic tablet computer. See [Appendix N](#) for an example.

The EQ-5D-5L is a standardized instrument for use as a measure of health outcome. It provides a simple descriptive profile and a single index value for health status, and is applicable to a wide range of health conditions and treatments. The EQ-5D-5L is available in many languages and it takes approximately 5 minutes to complete. EQ-5D-5L data will be captured using a portable electronic tablet computer. See [Appendix O](#) for an example.

It is important that every subject completes all assessments of EORTC QLQ-C30 and EQ-5D-5L at every specified time point, prior to dosing and prior to interaction with study personnel, to minimize missing data and subject bias.

[REDACTED]

[REDACTED]

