### **12.2. Emergency Identification of Investigational products**

This is an open-label study; therefore, IP will be identified on the package labeling.

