10.2.14. EORTC QLQ-C30 and EQ-5D-5L

For Phase 2, the analyses will address the mean differences by treatment arm on the EORTC QLQ-C30 scale and subscale scores and the treatment arm differences in the proportion of subjects who achieve minimal clinically important differences. The scoring for the EORTC QLQ-C30 and methods to address missing values will be accomplished according to directions provided by the instrument developer. The analyses of the EORTC QLQ-C30 will be based on all randomized subjects who completed the baseline assessment and had at least one post-baseline assessment with the EORTC QLQ-C30. The observed case method and the descriptive statistics will be used to summarize the observed scores and the change from baseline score by visit and the treatment arm for each domain of the QLQ-C30. In addition, frequency tables for categorized change from baseline scores (Improving, No Change, and Worsening) will be presented by treatment arm. A change of at least 10 points on the standardized domain scores will be required for it to be considered meaningful ([Osoba, 1998](#)).

For Phase 2, EQ-5D-5L will be scored according to the instrument guidance and analyzed accordingly. The EQ-5D-5L consists of 2 pages – the EQ-5D-5L descriptive system and the EQ Visual Analogue scale (EQ VAS). The descriptive system comprises of 5 dimensions: Mobility, Self-care, Usual Activities, Pain/Discomfort and Anxiety/Depression. Each dimension has 5 levels: no problems, slight problems, moderate problems, severe problems, and extreme problems. Responses from the 5 dimensions are coded so that a ‘1’ indicates no problem on that dimension, and ‘5’ indicates the most serious problem. The responses for the five dimensions can be combined in a five-digit number describing the respondent’s health state. For instance, a state of 11111 indicates no problem with any of the 5 dimensions, but a state of 55555 indicates the most difficulty on all 5. Missing and un-interpretable values (e.g. two responses are given for a single dimension) which are not recoverable through queries will be coded as ‘9’. These health states will be converted to a single index value using the crosswalk link function based on the existing value sets derived based on United Kingdom time trade-off (TTO) valuation techniques.

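### In open-label Phase 2 the first HRQoL questionnaires fall on Cycle 1 Day 1, up to 3 days after randomisation, so subjects can know their arm when they give the baseline for the change scores

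*Protocol*

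**What the plan says.** - **Blinding.** The Protocol Summary states: "The Phase 2 stage is an open-label randomized study". Section 12.2 adds: "This is an open-label study; therefore, IP will be identified on the package labeling".
- **Order of events.** Protocol Section 7.2.2.2 randomises through the IWRS once eligibility is confirmed. The Protocol Summary says: "Study treatment will start within 3 days of randomization". Footnote d of Table 4 gives the same order: "The subject should start study treatment (ie, Day 1 of Cycle 1) within 3 days after enrollment or randomization".
- **Questionnaire schedule.** The Table 4 row "EORTC QLQ-C30 and EQ-ED-5L" has a dash at screening and its first mark on Day 1 of Cycle 1. The table in SAP 17.3 repeats this. The screening list in Protocol Section 6.1 has no HRQoL item; the questionnaires first appear under the Treatment Period in Section 6.2.
- **Baseline rule.** Under Protocol Section 6.2.1, "results obtained just prior to the start of study treatment on Day 1 of Cycle 1 will serve as the baseline values". SAP 5.1 likewise takes the latest value before first dosing. Neither document sets a separate rule for HRQoL.
- **Safeguard.** Protocol Section 6.8 asks for completion at "every specified time point, prior to dosing and prior to interaction with study personnel, to minimize missing data and subject bias".
- **Analysis.** SAP 10.2.14 analyses QLQ-C30 "based on all randomized subjects who completed the baseline assessment and had at least one post-baseline assessment with the EORTC QLQ-C30". It summarises observed scores and change from baseline by visit and arm, and classifies QLQ-C30 changes as improving, unchanged or worsening with a 10-point threshold. EQ VAS and the EQ-5D index are summarised as values and as change. HRQoL against azacitidine alone is a stated Phase 2 secondary objective.

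**The concern.** A baseline for a randomised comparison should be something that allocation cannot influence. Here it can be. A subject who has just learned that the allocation is azacitidine alone, or the combination, may rate health differently for that reason.

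If that happens in one arm more than the other, part of the difference in change from baseline comes from the starting point rather than from treatment, and some subjects near the 10-point threshold change category. The instruments are not equally exposed. Appendix O asks about health today throughout, while most of the QLQ-C30 in Appendix N looks back over the past week.

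What is at stake is how the change-score results for one secondary objective are read. The primary endpoint, overall response rate, is not touched.

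**Working it through.** The plan gives no HRQoL sample size, standard deviation or expected difference, so there is no figure of its own to reproduce.

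**Step 1: can a scheduled HRQoL value precede allocation?**
- Randomisation is day 0, and Cycle 1 Day 1 is day 0 to day 3 (Table 4, footnote d).
- The first questionnaire is on Cycle 1 Day 1, before dosing (Table 4; Section 6.8).
- Section 6.2.1 falls back on the latest screening result if the Day 1 value is missing. For HRQoL that fallback is empty, since none is collected at screening.
- No section requires completion before the IWRS call or before the subject is told the arm.

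So the baseline is given between 0 and 3 days after allocation. With same-day randomisation, the order in Section 6.8 may put it before disclosure, but nothing requires this.

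**Step 2: what a reaction does to the change score.** Let *a* be the net between-arm shift in the baseline score caused by learning the arm, and *r* (0 to 1) the fraction still present at a later visit. In the shifted arm:

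- Cycle 1 Day 1 baseline: reported change = (true follow-up + r·a) − (true baseline + a) = true change − (1 − r)·a
- Pre-randomisation baseline: reported change = (true follow-up + r·a) − true baseline = true change + r·a

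The size of the error in the between-arm difference in change, in points, for assumed shifts of 2.5, 5 and 10:

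| Fraction persisting, r | Day 1 baseline, (1 − r)·a | Pre-randomisation baseline, r·a |
|---|---|---|
| 0 | 2.5 / 5 / 10 | 0 / 0 / 0 |
| 0.5 | 1.25 / 2.5 / 5 | 1.25 / 2.5 / 5 |
| 1 | 0 / 0 / 0 | 2.5 / 5 / 10 |

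The full shift enters the Day 1 change score only if the reaction has gone by the later visit.

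**Step 3: the QLQ-C30 categories.** Assume normally distributed changes with mean 0 and SD 20 to 30 points, and an error of *b* points toward improvement in one arm. The share reaching 10 points is 1 − Φ((10 − b)/SD).

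| Error b | SD 20 | SD 25 | SD 30 |
|---|---|---|---|
| 0 | 30.9% | 34.5% | 36.9% |
| 2.5 | 35.4% | 38.2% | 40.1% |
| 5 | 40.1% | 42.1% | 43.4% |
| 10 | 50.0% | 50.0% | 50.0% |

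All shifts and SDs are assumptions that show a range; none comes from the documents. The second table applies to QLQ-C30 only, because SAP 10.2.14 sets no change threshold for EQ-5D-5L.

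**The case against.** The strongest objection is that every later questionnaire is also answered open label. If the reaction to allocation lasts, it sits in both baseline and follow-up and cancels in the current change score, whereas a pre-randomisation baseline would bring it into the change. The table in Step 2 shows this. It stands as a limit on the size of the problem and on what the fix can achieve. It does not justify a baseline that allocation can influence: a lasting reaction is already in the post-baseline observed scores and cannot be scheduled away, while a contaminated starting point can.

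Three further limits also stand. The HRQoL methods are observed-case and descriptive, with no specified test. Post-baseline observed scores, which SAP 10.2.14 also reports, do not depend on when baseline was taken. Same-day randomisation together with the order in Section 6.8 may protect some subjects.

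A reader might also infer two things that the documents do not support:

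- *That randomised but untreated subjects lack the baseline that SAP 5.1 gives them.* This has no effect. The HRQoL set needs a post-baseline questionnaire, and untreated subjects have none scheduled: visits follow treatment cycles, and the end-of-treatment evaluation is for subjects who took at least one dose. A questionnaire on the day of randomisation would also meet that rule.
- *That a baseline-adjusted HRQoL model would be compromised.* The SAP plans no such model.

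**Conclusion.** The concern holds as an avoidable opening for bias in the HRQoL change scores and the QLQ-C30 10-point categories. It rests on the schedule alone: open label, first questionnaire on Cycle 1 Day 1, up to 3 days after randomisation, and no requirement to complete it before allocation.

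Its size is unknown. The error in the between-arm difference in change lies between zero, if the reaction persists fully, and the whole shift, if it fades completely. This assumes that the persisting fraction lies between 0 and 1. The direction is also unknown: a depressed control baseline that recovers would understate AG-221, and the opposite reaction would overstate it.

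A reader might go further and conclude that the HRQoL comparison is biased by a given number of points, or that its false-positive rate is inflated. The documents support neither: they contain no evidence of a shift and specify no HRQoL test. Nor do they show that every subject knew the arm at baseline, only that subjects could. This is a low-cost improvement to a descriptive secondary analysis.

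**What to change.** **Schedule and definition.** In Table 4 and Section 6.8, have Phase 2 subjects complete both questionnaires after eligibility is confirmed and before the IWRS randomisation call. In SAP 10.2.14, define that value as the HRQoL baseline. The Cycle 1 Day 1 questionnaire can be dropped or kept as a descriptive visit.

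**Cost.** One row of the schedule and a sentence in each document. By Section 6.8 the two instruments take 10 to 15 minutes plus about 5, so 15 to 20 minutes on the existing tablet; if the Day 1 questionnaire is dropped, this time is only moved earlier. A few subjects will complete them and then not be randomised.

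**Subjects already enrolled.** The latest amendment justification says that the primary clinical study report is final and that 15 subjects remained on treatment on 15 March 2021. Collected baselines cannot be changed. For these subjects, report by arm the interval from randomisation to the baseline questionnaire and the baseline scores, and state the limitation beside every change-from-baseline result. This needs only dates and scores that the trial already collects.
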